**PROSPECTIVE, COMPARATIVE ASSESSMENT OF ALVEOLAR RIDGE
PRESERVATION USING DIFFERENT BONE GRAFTING MATERIALS
(SYMBIOS CORTICAL-CANCELLOUS GRANULE MIX; SYMBIOS
OSTEOGRAF LD-300; OSTEOGRAF/N-300) FOLLOWING TOOTH
EXTRACTION**

NCT number NCT02532543
Document Date October 04, 2016

CLINICAL STUDY PROTOCOL

Study Product:

Study Code:

Date: October 4, 2016

PROSPECTIVE, COMPARATIVE ASSESSMENT OF ALVEOLAR RIDGE PRESERVATION USING DIFFERENT BONE GRAFTING MATERIALS (SYMBIOS CORTICAL-CANCELLOUS GRANULE MIX; SYMBIOS OSTEOGRAF LD-300; OSTEOGRAF/N-300) FOLLOWING TOOTH EXTRACTION

PROTOCOL SYNOPSIS

Principal Investigator

[name], MS

Co-Investigators

[name] [name], MS

[name], BDSc

[name]

Study Coordinator

[name]

Study center(s) and number of subjects planned

The study will include a total of 80 subjects recruited at the University of North Carolina, USA

Study timetable

Estimated date of first subject Q4 2015
enrolled

Estimated date of last subject Q3 2016
completed

Objectives

The primary objective of this study is to investigate volumetric osseous changes of an extraction socket at 3 months following a ridge preservation procedure using three different commercially available grafting materials (allograft, xenograft, and alloplast).

Secondary objectives include calculating linear horizontal and vertical bone and soft tissue changes.

Study design

The study is designed as a randomized controlled clinical trial. Immediately following tooth extraction, patients will be assigned to one of four treatment groups for ridge preservation. Groups will include the following:

- Group A (Symbios demineralized cortical-cancellous granule mix, Symbios OsteoShield Collagen Resorbable Membrane) (Allograft)
- Group B (Symbios OsteoGraf/LD-300, Symbios OsteoShield Collagen Resorbable Membrane) (Alloplast)
- Group C (OsteoGraf/N-300, Symbios OsteoShield Collagen Resorbable Membrane) (Xenograft)
- Group D (Symbios OsteoShield Collagen Resorbable Membrane only)

Target subject population

Patients in need of extraction and ridge preservation within zones 4-13, 20-22, and 27-29 will be included.

Investigational products

All products are intended to be used in an on-label procedure.

Symbios demineralized cortical-cancellous granule mix is an allograft bone graft material.

Symbios OsteoGraf LD-300 is an alloplastic bone grafting material composed of a low density synthetic hydroxyapatite.

OsteoGraf/N-300 is a xenoplastic bone grafting material that is a bovine-derived microporous hydroxyapatite.

Symbios OsteoShield Collagen Resorbable Membrane is a resorbable tissue matrix composed of Type-I Bovine collagen taken from the Achilles tendon. It presents as a multi-layer membrane which guides the healing of bone and the surrounding tissue, while the inner layers help prevent cellular and bacterial down growth into the site of bone preservation.

Duration of treatment

The study will be a 3 month follow-up. The treatment period includes tooth extraction followed by a ridge preservation procedure. Follow-up visits following the ridge preservation will occur at 14 days, and 3 months.

Outcome variables

Efficacy

Primary outcome variable:

- Volumetric osseous dimensional changes at 3 months

Secondary outcome variables:

- Horizontal and vertical dimensional changes in site (CBCT, cast measurements)
- Soft tissue dimensional changes (CBCT, cast measurements)

Patient reported outcomes

- Not applicable

Health economics

- Not applicable

Pharmacokinetics

- Not applicable

Safety

- Not applicable

Genetics

- Not applicable

Statistical methods

All primary and secondary outcome measurements will be analyzed by Wilcoxon rank sum test.

Membranes and bone replacement grafts are commonly used in ridge preservation procedures. A variety of bone graft options are available, including autogenic, allogenic, xenogenic, and alloplastic options, none of which have shown any superiority over another. The use of autogenic bone, however, requires a second surgical site, leading to increased treatment time and added patient morbidity. Instead, allografts, xenografts, and alloplasts are favored for ridge preservation procedures due to their convenience. Similarly, allogenic, xenogeneic, and alloplastic membranes have been used to seal extraction sockets, promoting a more ideal healing pattern, and reducing the amount of bone loss (6). What is unclear, however, is the effect of these different grafting materials in maintaining the ridge. Clarification of their unique influences, if any, of the maintenance of the post-extraction alveolus is necessary to help guide treatment decisions.

1.2 Rationale

This study is intended to provide statistically robust evidence that Symbios demineralized Cortical cancellous mix, Symbios OsteoGraf LD-300, and OsteoGraf/N-300 combined with Symbios OsteoShield Collagen Resorbable Membrane can adequately support the alveolus during ridge augmentation

procedures, reducing the dimensional changes of both the alveolus and the overlying soft tissues. Additionally, a comparison between each material will be made, providing further evidence of each materials' ability to preserve the alveolus. An additional comparison of the use of the Symbios OsteoShield Collagen Resorbable Membrane with or without supportive graft material will be made. These comparisons are intended to define in objective terms the response of the hard and soft tissues to ridge augmentation using four different protocols currently used in clinical practice. To fulfill the goals of this project, the clinical study will enroll sufficient patients to perform statistical analyses of primary objectives.

A common and non invasive approach used for site assessment following a grafting procedure is the use of cone-beam computed tomography (CBCT) images (7). Several studies have demonstrated the reproducibility and accuracy of CBCT(8-11); concluding that there was no significant difference between the radiographic and clinical measurements. CBCT is now acknowledged by the American Academy of Oral and Maxillofacial Radiology, for the pre-surgical implant planning and augmentation procedures as the imaging modality of choice for preoperative cross-sectional images of potential implant sites (12). CBCT may be used to measure the alveolar bone condition prior to implant therapy and following ridge preservation. Therefore, when serial CBCT data is available, the direct volumetric assessment of ridge preservation outcomes will be possible.

2 STUDY OBJECTIVES

2.1 Primary objective

The primary objective is to compare the volumetric changes in the osseous dimensions following a post-extraction ridge preservation procedure. Three different bone-grafting materials will be used, along with comparison to a non-grafted membrane only group. Data will primarily be obtained from DICOM images acquired by CBCT imaging. A surface based model will be constructed through image segmentation from both the pre- and post-operative CBCT images. The models will then be aligned/superimposed using a surface registration algorithm. Both images will be cropped to represent the same region of interest and the volumes will be calculated and compared.

Hypothesis: No significant differences in ridge volume maintenance are anticipated among the three grafting groups. The combined use of particulate graft material with a resorbable collagen membrane will maintain a greater ridge volume than the use of a resorbable collagen membrane alone.

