3.4 Method of assigning subjects to treatment groups

Subject numbers (subject ID) will be consecutively allocated in series at day of inclusion (Visit 1). Subjects will receive numbers starting at 101. Enrollment will continue until 80 subjects have been allocated a subject ID. If a subject discontinues, the subject number will not be reused.

Subjects will be randomized strictly sequentially at day of extraction and ridge preservation (Visit 2). At Visit 2 all study sites in all subjects are considered equivalent. The randomization schedule will be generated using a validated system under the responsibility of the investigatory team. 80 pieces of folded paper will contain the allocated treatment group (20 each of group A, B, C and D) and contained in an enclosed container. One piece of paper will be blindly selected by the PI or co-investigators, and the treatment group will be revealed to the clinician only following extraction of the tooth.

The randomization code papers will be stored in an enclosed and concealed container and stored by PI and co-investigators.

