6.2 Method of statistical analysis

6.2.1 Primary objective

The primary objective is to compare dimensional bone changes from baseline (Visit 2) to three months (Visit 4) occurring in a single bound extraction site following ridge preservation using three different grafting materials and membrane, and one no graft membrane only group.

Assume the change is denoted C_A , C_B , C_C , and C_D , for group A, B, C, and D respectively. The null-hypothesis is then to test if:

$H_0: C_A = C_i$ ($i = B, C$, and D respectively)
can be rejected and hence
 $H_1: C_A \neq C_i$ ($i = B, C$, and D respectively)
accepted.

H_0 will be tested by means of the Wilcoxon rank sum test. A p-value less than 0.05 will be regarded statistically significant.

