6.3 Determination of sample size

A sample size of 20 participants per treatment group was selected following power calculations and allowing for 10% patient dropout (has dropout rate been factored into our sample size of 20 patients per group). A sample size of 18 patients was calculated for the primary outcome variable (horizontal bone changes) with the assumption that the detectable difference would amount to 0.5mm³ with a standard deviation of 0.5. The type I error probability was set at 0.05 and the statistical power was set at 80%.

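### Half of the primary hypothesis is that the three grafts do not differ, but the plan has only a difference test at 0.05, leaves out B vs C, and makes confidence intervals optional

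*Combined protocol and SAP*

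**What the plan says.** Section 2.1 puts a two-part hypothesis under the primary objective. The first part concerns the grafts: "No significant differences in ridge volume maintenance are anticipated among the three grafting groups". The second part is that graft plus membrane keeps more ridge volume than membrane alone.

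Section 6.2.1 sets equality as the null hypothesis and a two-sided difference as the alternative, for group A against B, C and D in turn. The rule is: "H_0 will be tested by means of the Wilcoxon rank sum test. A p-value less than 0.05 will be regarded statistically significant". B against C is not listed. Section 1.2 nevertheless says that the materials will be compared with one another, and the hypothesis in 2.1 covers all three.

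Section 6.1 permits confidence intervals beside p-values but does not require them. No equivalence margin or interval-based rule appears anywhere. Section 6.1 also makes a separate, fuller SAP optional.

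Section 6.3 sizes the trial to find a difference: "detectable difference would amount to 0.5mm³ with a standard deviation of 0.5", with two-sided 0.05 and 80% power, giving 18 evaluable per group. It then states: "A sample size of 20 participants per treatment group was selected following power calculations and allowing for 10% patient dropout".

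**The concern.** A test for a difference can support a claim of difference. Failing to reject does not support a claim of no difference, because a small or noisy trial fails to reject often whatever the truth. Here the expected result for the grafts is worded in terms of significance, and the only planned output is a p-value. A report that follows the plan to the letter could therefore offer p≥0.05 as bearing out the first half of the hypothesis, and low precision would make that outcome more likely.

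Section 1.1 says that the separate effects of these materials need clarifying to guide treatment decisions. For that purpose a reader needs to know how large a difference between two grafts remains possible, and for B vs C the plan does not provide even a p-value.

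**Working it through.** **Inputs.** From 6.3: difference 0.5, SD 0.5, alpha 0.05, power 80%, 18 evaluable and 20 randomised per group. From 6.2.1: two-sided Wilcoxon rank sum test. Assumed here: normally distributed changes with equal SDs. The 0.5 SD and 0.75 SD differences below are illustrations; the documents do not call either important.

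**1. The plan's own figure.** The standardised difference is 0.5/0.5 = 1.0 SD.
- Normal approximation: n = 2(1.960 + 0.842)²/1.0² = 15.7, so 16 per group.
- Two-sample t-test: 16.71, so 17.
- Wilcoxon, with relative efficiency 0.955: 16.71/0.955 = 17.5, so 18.
- Simulated Wilcoxon power at 1.0 SD (20,000 runs): 78.4% with 17 per group, 80.2% with 18.
- Dropout: 18/0.90 = 20.

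The 18 and the 20 are reproduced for the planned test.

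**2. Chance of p≥0.05 for one pair.** By the normal approximation this is Φ(1.960 − d√(n/2)), with d in SD units. At d = 0.5:
- n = 18: Φ(1.960 − 0.5 × 3.000) = Φ(0.460) = 67.7%
- n = 20: Φ(1.960 − 0.5 × 3.162) = Φ(0.379) = 64.8%

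| True difference | n per group | Normal | t-test | Wilcoxon (simulated) |
|---|---|---|---|---|
| 0.5 SD | 18 | 67.7% | 69.2% | about 71% |
| 0.5 SD | 20 | 64.8% | 66.2% | about 68% |
| 0.75 SD | 18 | 38.6% | 41.1% | about 44% |
| 1.0 SD | 18 | 14.9% | 17.0% | about 20% |
| 1.0 SD | 20 | 11.5% | 13.1% | about 15% |

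**3. All the graft tests together.** If at least one pair differs by 0.5 SD, the chance that every test is non-significant is 52 to 64% over all three pairs. Over the two listed tests (A vs B, A vs C) it is 53 to 80%, depending on which graft differs. It is highest when B and C differ by 0.5 SD with A midway: each listed test then faces only 0.25 SD, and the pair that differs is not tested.

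**4. What the interval can exclude.** The 95% half-width in SD units, t-based, is t(0.975, 2n−2) × √(2/n).
- n = 18: 2.032 × 0.333 = 0.68
- n = 20: 2.024 × 0.316 = 0.64

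At n = 18, an observed difference below 1.00 − 0.68 = 0.32 SD excludes 1.0 SD. One between 0.32 and about 0.68 SD is non-significant and does not exclude it. At the upper end the interval reaches 2 × 0.677 = 1.35 SD. In simulation at a true 0.5 SD with 18 per group, 58% of the non-significant results had a t-based 95% interval that still included 1.0 SD.

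**5. Would ±1.0 SD serve as a similarity margin?** Suppose two grafts were called similar when the 90% interval lies inside ±1.0 SD. Grafts that truly differ by 0.5 SD would be called similar about 40% of the time at n = 18 and 44% at n = 20. Under true equality, the Hodges-Lehmann interval at n = 18 meets the rule about 77 to 78% of the time for one pair, but only 54% for all three together. A margin of ±0.5 SD would need 2(1.645 + 1.282)²/0.5² = 68.5, so 69 per group. At 18 to 20 per group the 90% half-width of 0.56 to 0.53 SD already exceeds that margin.

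**The case against.** The strongest reply is that the plan never claims equivalence. Section 2.1 says what is anticipated, which is a prediction, and the stated objective is to compare. Section 6.2.1 speaks of rejecting the null hypothesis and never of accepting it. Section 6.1 already allows intervals and requires descriptive statistics by variable, and section 4.2.1.1.2 says that average changes will be compared among the groups.

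Much of this stands. A reader might infer that the plan treats p≥0.05 as confirmation, or as showing the grafts interchangeable; no section says so. A reader might also infer that a non-significant result can never exclude the plan's detectable difference. That is too strong, because an observed difference below about 0.32 SD does exclude 1.0 SD at n = 18. Nor is the figure near 70% the chance for the whole three-graft hypothesis: it applies to one pair at an illustrative difference. At the plan's own 1.0 SD the test misses only about 15 to 20% of the time.

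The gap is still not filled. The prediction is labelled as half of the primary hypothesis, and no other means of judging it is given. Intervals are optional and tied to no interpretation, and section 4.2.1.1.2 names no pairs and no rule.

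**Conclusion.** The concern holds in a limited form. As written, the plan can speak to the no-difference half of its primary hypothesis only through failure to reject, and it lists no test for one of the three graft pairs. For one pair truly 0.5 SD apart, non-significance is the likelier result (about 68 to 71%), and it often leaves 1.0 SD within the interval.

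These figures rest on normal data, equal SDs and 18 to 20 evaluable per group. They depend only on the standardised difference, so they do not turn on the fact that 6.3 names horizontal bone change while giving a volume unit. The second half of the hypothesis, graft against membrane alone, is not affected by this point. The change should be made: it is cheap and alters no treatment, visit or sample size.

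**What to change.** - **Section 6.2.1:** add B vs C to the listed comparisons.
- **Sections 6.1 and 6.2.1:** for A–B, A–C and B–C, require the Hodges-Lehmann difference in volume change with its 95% confidence interval, in place of the optional wording in 6.1 for these pairs.
- **Sections 2.1 and 6.2.1:** state that p≥0.05 is not evidence of similarity. The graft comparison will be interpreted from the interval, that is, from the largest difference in either direction that the data do not exclude.
- **Margin:** do not adopt ±1.0 SD. It comes from the calculation for detecting a difference, and nothing in the documents justifies it as small enough to ignore. Any formal similarity claim needs a margin that the sponsor justifies in advance in the unit of the primary outcome. The documents give no SD that is clearly for volume change, so that margin cannot be derived from them.

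The cost is one extra comparison and three intervals from data already collected. The downside is that some graft comparisons may have to be reported as inconclusive.

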2.2 Secondary objectives

Secondary objectives of the study are to evaluate and compare:

- Buccolingual dimensional changes in site (CBCT)
- Vertical dimensional changes in site (CBCT)
- Soft tissue contour changes associated with healing post extraction (digitized cast measurements superimposed on CBCT images)

3 STUDY PLAN AND PROCEDURES

3.1 Overall study design and flow chart

The study is designed as a randomized controlled prospective clinical trial.

[figure not shown]
The study population will consist of individuals requiring an extraction with socket preservation. Sites within zones 4-13, 20-22, 27-29 will be included.

80 subjects will be included. Each subject will be randomized into one of three bone graft treatment groups or one membrane only treatment group:

- Group A (Symbios demineralized cortical-cancellous granule mix, Symbios OsteoShield Collagen Resorbable Membrane) (Allograft)
- Group B (Symbios OsteoGraf/LD-300, Symbios OsteoShield Collagen Resorbable Membrane) (Alloplast)
- Group C (OsteoGraf/N-300, Symbios OsteoShield Collagen Resorbable Membrane) (Xenograft)
- Group D (Symbios OsteoShield Collagen Resorbable Membrane only)

The study will be a 3 month follow-up with 4 clinic visits.

Figure 1 Study flow chart

3.1.1 Visit 1: Screening

Subjects in need of a single tooth extraction and ridge preservation of a single tooth bound by adjacent teeth that are deemed eligible by meeting inclusion and exclusion criteria will be considered for treatment in this study. The tooth requiring extraction must lie within the region 4-13, 20-22, 27-29 (maxillary or mandibular first premolar or anterior tooth, excluding mandibular incisors).

Before any assessment or examination is carried out the subject must have been informed orally and in writing about the study, and have signed the appropriate clinical and study consent forms. Informed consent for the research study will be given and signed on paper, as well as HIPAA authorization. Subjects will also be asked to sign informed consent documents.

Individuals meeting all inclusion and exclusion criteria and that have signed all appropriate consent forms will be further evaluated. A clinical exam will entail evaluation of general dental and systemic health. It will also include a clinical and radiographic assessment of the tooth to be removed and the adjacent teeth, which is standard of care. Pre-existing radiographs (e.g. panoramic and intraoral) can be used but must not be older than 6 months. An impression will be made using an elastomeric impression material of the planned extraction site to allow fabrication of a temporary tooth (standard clinical requirement). This impression will also serve an additional research purpose, providing baseline tissue data. Subjects will immediately be scheduled for Visit 2 provided that they fulfill all inclusion and exclusion criterion.

A radiographic stent for research purposes will be fabricated using the model obtained from the initial impression to aid in image alignment, superimposition and identifying the points of measurement for the study objectives.

After pre-surgical evaluation and planning, patients will be enrolled and randomly allocated treatment into treatment group A, B, or C; or into group D.

[figure not shown]
This visit includes all procedures, which are standard clinical protocol, with additional usage of the clinical impression for research purposes.

3.1.2 Visit 2: Extraction, Initial CBCT, and Socket Preservation Surgery

Randomization and Stratification

Subjects meeting all inclusion and none of the exclusion criteria will be randomly allocated to group A, B, C, or D, through the blind drawing out of a folded piece of paper containing the assigned treatment group (20 pieces indicating group, A, B, C and D) by the PI or co-investigators. Subjects will be randomized into treatment groups immediately following tooth extraction.

Figure 2 Randomization and stratification

Pre-Surgical, Surgical, and Post-Surgical Care (at surgical appointment)

Pre-surgical, surgical and post-surgical care will be given at the discretion of the Investigator and recorded in appropriate sections in the CRF:

- Antibiotics
- Analgesics
- Anaesthesia
- Anxiolysis

Antibiotics:

Pre-surgical antibiotic prophylaxis will be provided for patients at risk for infective endocarditis or with total joint replacement according to current guidelines provided by the American Dental Association, American Heart Association (13), and the American Academy of Orthopaedic Surgeons (14).

Post-surgical antibiotic coverage will be provided to patients. It is anticipated that a 7-day course of 500mg Amoxicillin every 8 hours or 300mg Clindamycin every 6 hours will be provided.

Analgesics:

Post-surgical analgesics will be provided, most likely consisting of 800mg Ibuprofen every 6-8 hours and 5/325mg Acetaminophen/Hydrocodone every 4-8 hours.

Anxiolysis:

Options will be discussed with the patient and a decision will be made to reduced anxiety using 1-2mg Ativan.

Anesthesia:

20% benzocaine topical anesthesia will be maintained for 1 minute. Infiltration anesthesia using 2% lidocaine with 1:100,000 and 2% lidocaine with 1:50,000 epinephrine will be provided. It is anticipated that 1.8 to 3.6cc will be used.

Post-surgery, infiltration anesthesia with 0.5% bupivacaine with 1:200,000 will be provided. It is anticipated that 1.8cc will be used.

All medications used are standard clinical practices.

Pre-Surgical Procedures

Buccal and crestal photographs of the planned surgical site will be obtained using a Canon 50D digital camera body with a Canon 100mm f/2.8 macro lens and a Canon MR-14EX macro ring flash.

All pre-surgical procedures including photographs taken are standard clinical practice in the School of Dentistry clinics.

Surgical Procedure

A circumferential sulcular incision will be placed around the teeth to be extracted. Periotomes and luxators will be used to extract the tooth with minimal trauma to the adjacent tissues. The socket wall will be examined for any dehiscence greater than 3mm or fenestrations. If these are present, the patient will be excluded from the study. Gauze will be placed in the area to produce wound hemostasis

Immediately following tooth extraction, the patient will have a small field-of-view cone beam computed tomography (CBCT) image produced whilst wearing the radiographic stent. Images will provide pre-preservation data for horizontal and vertical bone locations.

Following CBCT imaging, a ridge preservation procedure will be completed as follows:

- Group A: Symbios demineralized cortical-cancellous granule mix reconstituted in sterile saline will be used to augment the socket and will be covered by a Symbios OsteoShield Collagen resorbable membrane.
- Group B: Symbios OsteoGraf LD-300 reconstituted in sterile saline will be used to augment the socket and will be covered by a Symbios OsteoShield Collagen resorbable membrane.
- Group C: Symbios OsteoGraf/N-300 reconstituted in sterile saline will be used to augment the socket and will be covered by a Symbios OsteoShield Collagen resorbable membrane
- Group D: Socket covered with Symbios OsteoShield Collagen resorbable membrane and no grafting material, allowing socket to heal.

Grafted sockets will be closed with a barrier membrane using 5-0 chromic gut suture. It is anticipated that a cross mattress and/or simple loop sutures will be employed.

All surgical procedures listed above are standard clinical procedures, including preparation and utilization of grafting materials list above.

Post-Surgical Procedures

Buccal and crestal photographs of the surgical site will be obtained, which is standard clinical practice in the School of Dentistry.

Standard UNC post-operative instructions will be given which includes the use of a Chlorhexidine rinse 2 times daily for 2 weeks.

This visit includes a CBCT for research purposes only. The remainder of treatment is standard clinical protocol.

